9.3.3 SAFETY

This population is defined as any participant enrolled in the study who receives a device. At any time during the study, if a participant's clinician deems it necessary to end medication treatment, or, conversely, to begin treatment, that participant's cohort will be determined based on where the participant spent the majority of the first treatment phase (the tiebreaker will be cohort the participant belonged to on Day 28).

9.4 STATISTICAL ANALYSES

9.4.1 GENERAL APPROACH

All continuous variables will be summarized as means (standard deviations), medians (25th and 75th percentiles), minimum and maximum. The number and percentage of participants in each category will be presented for categorical variables. Shift tables may be used to compare baseline and post-baseline assessments involving categorical variables.

Statistical comparisons of continuous variables within each of the two cohorts will be performed using a paired *t*-test, with a Box-Cox transformation applied to induce normality if necessary; comparisons of categorical variables will be performed using the Pearson's chi-square test or Fisher's exact test depending on expected cell sizes. Statistical normality will be assessed using a Shapiro-Wilk test, and will be confirmed by examining the corresponding diagnostic figures. Unless otherwise indicated, comparisons will always use a two-sided significance test at the 95% level of confidence.

All analyses will be conducted using a complete case analysis. In no situation will missing data be imputed.

Analyses will be performed using SAS software version 9.2 or higher (SAS Institute, Inc., Cary, NC).

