Exploratory/Descriptive Sustained benefits, through reduction of ADHD impairment and symptoms, following 1-Month of AKL-T01 treatment (with AKL-X01 symptom tracking) (both Cohort 1 and Cohort 2).	
Exploratory (Cohort 1, Cohort 2):
 
 1) Overall change in clinician-reported IRS “Overall severity of child’s problem in functioning and overall need for treatment” score from baseline to Day 56 and from baseline to Day 84. 2) Overall change in ADHD-RS total component score from baseline to Day 56 and from baseline to Day 84. 3) CGI-I score at Day 56 and at Day 84. 4) Overall improvement in TOVA ACS and certain constituent scores, from baseline to Day 56 and from baseline to Day 84. 5) Overall change in Test of Silent Reading Efficiency and Comprehension (ToSREC) from baseline to Day 28 and from baseline to Day 84, using the appropriate ToSREC form. 6) Overall change in Mathematics Fluency and Calculation Tests (MFaCTs) from baseline to Day 28 and from baseline to Day 84, using the appropriate MFaCTs form. 
Descriptive (Cohort 1, Cohort 2):
 
 1) AKL-X01 usage, as compared to the expected usage of 5 days per week. 2) Participant/Caregiver experience and preference questionnaires. 3) Participant demographics. 4) Reported adverse events. 5) Change in participant’s medications. 6) Constituent measures of the IRS (individual questions), ADHD-RS (sub-scales and individual questions), and TOVA. 	
Measuring the overall change from baseline to Day 84 will examine the sustained effects of AKL-T01 on ADHD symptoms after 1-Month of treatment and 1-Month break, and a follow-on month of treatment in both Cohorts 1 and 2 (analyzed individually).
 
Measuring the overall change from baseline to Day 56 will examine the sustained effects of AKL-T01 on ADHD symptoms after 1-Month of treatment and 1-Month break in both Cohorts 1 and 2 (analyzed individually).

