4 STUDY DESIGN

4.1 OVERALL DESIGN

This study is a multi-center, open label trial to determine the effect of AKL-T01 treatment (with AKL-X01 mobile app-based symptom tracking) on ADHD symptoms and impairments in children currently on or off stimulant.

Two hundred and three participants (203) at multiple sites will be enrolled into 2 cohorts. 130 participants will be recruited into cohort 1 and 73 participants will be recruited into cohort 2.

Cohort 1 will have been stable** on stimulant(s) for at least 30 days before baseline. At screening (at least 7 and up to 30 days before baseline), participant caregivers will be instructed to download AKL-X01 on to their smartphone. Caregivers will use AKL-X01 for tracking participants' symptoms and behaviors beginning between days -30 and -7, through day 84. During Treatment Phase 1, Days 1 through 28, participants will continue receiving stimulant and will also receive AKL-T01 treatment. During the 1-month treatment pause, Days 29 through 56, participants will continue receiving stimulant but will discontinue AKL-T01. During Treatment Phase 2, Days 57 through 84, participants will continue receiving stimulant and will also receive AKL-T01 treatment.

****Note:** Medication stability is defined as:

- Moderate response on stimulant, but still room for improvement
- Dose unchanged within past 30 days, but other doses have been tried previously without improvement
- Currently taking stimulant, but parent and/or caregiver wishes not to increase dosage for any reason
- Taking consistent stimulant dose on weekdays, but not on weekends

The hypothesis for Cohort 1 is that children receiving stimulant plus AKL-T01 treatment will improve in ADHD symptoms and impairments from Day 0 to Day 28.

Cohort 2 will have been stable without any stimulant for ≥ 30 days before baseline. At screening (at least 7 and up to 30 days before baseline), participant caregivers will be instructed to download AKL-X01 on to their smartphone. Caregivers will use AKL-X01 for tracking participant symptoms and behaviors beginning between days -30 and -7, through day 84. During Treatment Phase 1, Days 1 through 28, participants will receive AKL-T01 treatment. During the 1-month treatment pause, Days 29 through 56, participants will discontinue AKL-T01. During Treatment Phase 2, Days 57 through 84, participants will receive AKL-T01 treatment.

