9.2 SAMPLE SIZE DETERMINATION

Sample size estimates were computed by hand and verified with PASS (Machin, Campbell, Fayers, & and Pinol, 1997) (Zar, 1984). Assuming a standard deviation of 1, we determined that an effective total of at least 117 medicated participants (Cohort 1) would be needed to demonstrate an effect size of 0.30 with 90% power at the 95% level of confidence using a within-group *t*-test. Similarly, at least 66 non-medicated participants (Cohort 2) would be needed to demonstrate an effect size of 0.40 with 90% power and 95% confidence. Incorporating a 10% dropout requires that at least $130 + 73 = 203$ patients are enrolled in the study. See Table 1 below for more details.

Table 1. Sample size estimates for various combinations of differences and standard deviations. In all cases, we assume 90% power and 95% confidence. The rows used to inform enrollment size for this trial have been highlighted in gray.

Absolute difference between follow-up and baseline	SD	Effect Size	Effective n
0.30	1.00	0.30	117
0.30	1.50	0.20	263
0.30	2.00	0.15	467
0.35	1.00	0.35	86
0.35	1.50	0.23	193
0.35	2.00	0.18	343
0.40	1.00	0.40	66
0.40	1.50	0.27	148
0.40	2.00	0.20	263
0.45	1.00	0.45	52
0.45	1.50	0.30	117
0.45	2.00	0.23	208
0.50	1.00	0.50	42
0.50	1.50	0.33	95
0.50	2.00	0.25	168

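### Section 9.4.1 names only independent-groups tests for categorical comparisons, although the one categorical comparison it describes is paired; a wrong default of minor consequence

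*Combined protocol and SAP*

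**What the plan says.** Section 9.4.1 (General Approach) first deals with summaries. For categorical variables it provides counts and percentages, and adds that "Shift tables may be used to compare baseline and post-baseline assessments involving categorical variables".

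Its next paragraph deals with tests. "Statistical comparisons of continuous variables within each of the two cohorts will be performed using a paired" *t*-test, with a transformation if needed. After a semicolon, the same sentence says that "comparisons of categorical variables will be performed using the Pearson's chi-square test or Fisher's exact test", the choice between the two resting on the expected cell counts. Unless otherwise indicated, "comparisons will always use a two-sided significance test at the 95% level of confidence".

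The design has no control arm. Section 4.1 states: "This study is a multi-center, open label trial to determine the effect of AKL-T01 treatment". The hypotheses in Section 9.1 concern mean change within a cohort, and Section 9.4.2 reports results by cohort. No test between the cohorts is specified. McNemar, Bowker, Stuart-Maxwell or any other paired categorical test appears nowhere.

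**The concern.** Pearson's chi-square and Fisher's exact test need independent observations. A child's category at baseline and at Day 28 are two observations on one child and will usually be positively correlated. There are two ways to apply these tests to such data, and neither answers the question asked.

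- **Visit-by-category table.** Each child is counted twice, once per visit. The test treats the two rows as different children, overstates the variance of the difference, and gives p-values that are too large.
- **Shift table.** Each child is counted once, baseline category by follow-up category. The test asks whether baseline predicts follow-up. It can be highly significant when nothing has changed.

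In a study without a control arm, change over time is the only effect measure. The general rule for testing change in a category should therefore be a valid one.

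**Working it through.** **The plan's own figures.** The plan gives no figure for any categorical test. The cohort sizes used below come from Section 9.2 ("Assuming a standard deviation of 1", two-sided 5%, 90% power), and they reproduce with n = ((1.960 + 1.282) × SD / difference)²:

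- Cohort 1: (3.2415 / 0.30)² = 116.7, so 117.
- Cohort 2: (3.2415 / 0.40)² = 65.7, so 66.

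These sizes were set for the *t*-test and serve here only as realistic values of n. Category rates and the within-child correlation ρ are not in the plan. They are assumptions, with ρ run from 0 to 0.7.

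**Why the visit-by-category table fails.** With the same proportion p at both visits, the true variance of the difference is 2p(1 − p)(1 − ρ)/n. Pearson's test uses 2p(1 − p)/n. At nominal 5%, its large-sample size is therefore 2[1 − Φ(1.96/√(1 − ρ))]:

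- ρ = 0: 5.0%
- ρ = 0.3: 1.96/0.837 = 2.34, size 1.9%
- ρ = 0.5: 1.96/0.707 = 2.77, size 0.6%
- ρ = 0.7: 1.96/0.548 = 3.58, size 0.03%

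**Simulation** (40,000 data sets per setting). Size is for 50% at both visits. Power is for a change from 60% to 45%. McNemar is the asymptotic form without continuity correction.

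| n | ρ | Size, Pearson by visit | Size, McNemar | Pearson on shift table, no change | Power, Pearson by visit | Power, McNemar |
|---|---|---|---|---|---|---|
| 117 | 0.3 | 2.2% | 4.8% | 91% | 68% | 78% |
| 117 | 0.5 | 0.7% | 5.4% | >99% | 72% | 91% |
| 117 | 0.7 | 0.1% | 5.0% | 100% | 76% | >99% |
| 66 | 0.3 | 1.6% | 5.4% | 70% | 37% | 55% |
| 66 | 0.5 | 0.5% | 5.0% | 99% | 35% | 69% |
| 66 | 0.7 | 0.04% | 4.3% | 100% | 30% | 93% |

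A second set-up, a bivariate normal variable cut at each visit with latent correlation 0.6 and n = 117, agrees. Under no change at 50%, Pearson by visit rejects 1.4% of the time, Pearson on the shift table 99.6% and McNemar 5.1%. For a fall from 50% to 40%, power is 32% for Pearson by visit and 50% for McNemar.

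**Worked tables (assumed counts).**

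- n = 117, from 90 to 77 children in a category, with 20 leaving and 7 entering. Pearson by visit: z = (13/117)/√(0.7137 × 0.2863 × 2/117) = 1.88, p = 0.060 (Fisher 0.082). McNemar: (20 − 7)²/27 = 6.26, p = 0.012 (exact 0.019).
- n = 66, from 52 to 42, with 14 leaving and 4 entering. Pearson p = 0.055 (Fisher 0.083). McNemar: (14 − 4)²/18 = 5.56, p = 0.018 (exact 0.031).
- n = 117 with no net change, shift-table cells 70, 10, 10 and 27. Pearson: 117 × (70 × 27 − 10 × 10)²/(80 × 37 × 80 × 37) = 42.8, p = 6 × 10⁻¹¹. McNemar p = 1.00.

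**Where the rule could apply.**

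- Primary endpoint: paired *t*-test, or Wilcoxon signed-rank if skewed (9.1, 9.4.2).
- Secondary endpoints, CGI-I included: the primary technique (9.4.3).
- Exploratory endpoints: descriptive (9.4.9).
- Usage, questionnaires, demographics and medications: tables or listings (9.4.5).
- IRS and ADHD-RS components, CGI-S and CGI-I: descriptive tables by visit (9.4.8).
- Safety: listings and a table (9.4.4).

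What is left is any other categorical pre-post test, for example among the additional analyses that Section 9.4.2 allows investigators to request.

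**The case against.** The strongest reply is that the plan never assigns a chi-square test to paired data. The phrase about each of the two cohorts belongs to the continuous clause; the categorical clause mentions neither visits nor pairing. Sub-group details are left to the SAP (9.4.7), and Pearson or Fisher would be correct for comparing independent sub-groups. The remark in Section 3 that the cohorts are analysed individually concerns the Day 56 and Day 84 endpoints, which are descriptive. All of this stands, and it is why the paired reading has to be called an inference. It does not rescue the section: on either reading, the baseline-to-follow-up comparison that 9.4.1 describes has no valid test named for it.

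Two stronger readings are tempting, and the documents support neither.

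- A reader might infer that planned results will carry wrong p-values. No planned categorical pre-post p-value can be identified. The Schedule of Activities collects CGI-S only at baseline and CGI-I only afterwards, so neither forms a pre-post pair. C-SSRS is taken at screening and Day 84, but no test is assigned to it.
- A reader might infer that shift tables will be tested by chi-square and nearly always come out significant. Shift tables are optional and stand in the paragraph on summaries, and no text attaches a test to them. The shift-table column shows what would happen if someone did so.

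**Conclusion.** The point holds as a wrong default rule of minor severity. The only tests that Section 9.4.1 names for categorical comparisons are unsuited to the one categorical comparison it describes. If the default were followed on a visit-by-category table, it would be conservative and lose power: in the settings simulated, between 10 percentage points (n = 117, ρ = 0.3: 68% against 78%) and 63 points (n = 66, ρ = 0.7: 30% against 93%). These sizes rest on assumed category rates, assumed positive correlations and a binary variable; only n comes from the plan. At ρ = 0 the problem disappears. The primary and secondary analyses and the sample size are untouched.

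**What to change.** In Section 9.4.1, or in the SAP, replace the categorical clause with wording to this effect: any test of change in a categorical variable from baseline to a later visit will use McNemar's test for binary variables (exact when discordant pairs are few), the Stuart-Maxwell or Bowker test for variables with more than two unordered categories, and the Wilcoxon signed-rank test for ordinal variables; Pearson's chi-square or Fisher's exact test will be used only to compare independent participants. It would help to add that shift tables are descriptive unless one of these paired tests is named.

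The cost is one or two sentences. No new data, visits or participants are needed, and no primary or secondary analysis changes.

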9.4.2 ANALYSIS OF THE PRIMARY EFFICACY ENDPOINT(S)

The primary efficacy endpoint for each participant is the change in IRS score from baseline to Day 28, defined as the score on Day 28 minus the score at baseline. Missing data will not be imputed. If a participant is missing either the baseline or Day 28 IRS assessment, that participant will be excluded from the analysis. Within each cohort, the ITT population is the primary efficacy analysis population. Additional per-protocol analyses will be performed on the per-protocol population.

Statistical significance of the change in IRS will be determined using a paired *t*-test. No adjustment for covariates will take place for the primary efficacy analysis, although additional analyses may be requested at the discretion of the investigators. Details will be provided in the SAP.

The results of the primary efficacy analysis will be summarized by cohort as mean change (95% confidence interval) and p-value. If the upper bound of the 95% confidence interval is smaller than 0 in a particular cohort, we will conclude that significance is achieved within that cohort.

Outliers will be determined clinically and identified by an independent third party, with confirmation coming from the PI. If outliers are identified for a given endpoint, a sensitivity analysis will be performed without the outlier.

9.4.3 ANALYSIS OF THE SECONDARY ENDPOINT(S)

The following secondary efficacy endpoints will be tested using the same technique outlined for the primary efficacy analysis: (1) change in sum of ADHD-RS component scores from baseline to Day 28; (2) CGI-I score at Day 28; and, (3) change in TOVA ACS and certain constituents, from baseline to Day 28. The ITT population will be used for all secondary efficacy endpoints with the same analyses being repeated on the per-protocol population.

Family-wise error rate will be controlled using a hierarchical testing strategy. Within each cohort, the maximum allowable Type I error rate will be set to 0.05.

If the primary efficacy endpoint is significant at the 0.05 confidence level, the secondary efficacy endpoints will be tested sequentially in the order in which they appear above, starting with (1) change in autocalculated sum of ADHD-RS Total. If the test for (1) is significant at the 0.05 confidence level, the test for (2) CGI-I score at Day 28 will proceed. If the test for (2) is significant at the 0.05 confidence level, the test for (3) change in TOVA constituents from baseline to Day 28 will proceed, starting with Ex-Gaussian Tau Total, and then to API/ACS, Commission Errors Standard Score H2, RT Variability Standard Score Total, RT Mean Standard Score H1, D-Prime Standard Score H2, and Omission Errors Standard Score H2, in this order. At any point, if the test of a secondary efficacy endpoint fails to achieve significance at the 0.05 confidence level, only nominal p-values will be reported for that endpoint and for all subsequent secondary efficacy endpoints.

If the primary efficacy endpoint is not significant at the 0.05 confidence level, only nominal p-values will be reported for all secondary efficacy endpoints.

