9 STATISTICAL CONSIDERATIONS

This section provides a brief overview of the statistical analyses, both quantitative and qualitative in nature that will be used during this study. In addition to what follows in this section, further details will be provided in a separate statistical analysis plan (SAP).

The primary objectives of this study are to (1) understand the synergistic impairment effects when combining AKL-T01 (with app-based symptom tracking, AKL-X01) as adjunctive treatment to stimulant medication, and (2) understand the impairment effects of AKL-T01 (with app-based symptom tracking, AKL-X01) treatment in participants not recently on stimulant medication. Within both the medicated and non-medicated cohorts, a change in Impairment Rating Scale (IRS) (Clinician Report) from baseline to Day 28 will demonstrate the overall effect that AKL-T01 treatment has on ADHD symptoms.

The secondary objective of this study is to understand the symptom and attentional effects of AKL-T01 (with app-based symptom tracking AKL-X01) treatment in all participants. There is an additional exploratory objective which focuses specifically on sustained benefits, through reduction of ADHD symptoms and impairment, experienced by participants following (a) 1-month of treatment with AKL-T01, and (b) an additional 4 weeks of AKL-T01 treatment.

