9.1 STATISTICAL HYPOTHESES

The aim of the primary objective is to demonstrate a statistically significant difference on mean change in IRS “Overall severity of child’s problem in functioning and overall need for treatment” score, defined for each participant as the score measured on Day 28 minus the score measured at the baseline visit. In both the medicated and non-medicated cohorts, the statistical significance of the primary efficacy analysis will be assessed using a 2-sided paired *t*-test evaluated at the 95% level of confidence. The formulation of the null (H_0) and alternative (H_a) hypotheses are stated below, where μ_d refers to the true mean difference:

- $H_0: \mu_d = 0$
- $H_a: \mu_d \neq 0$.

If, within a particular cohort, the upper bound of the 95% confidence interval around the sample difference is smaller than 0, we will have sufficient evidence to reject H_0 and conclude that AKL-T01 plus Fengo improves ADHD symptoms in that cohort.

If the set of sample differences is non-normal, defined here as skewness larger than 1.5 in magnitude, the efficacy analysis will proceed as a non-parametric Wilcoxon signed rank test. Significance will be determined by evaluating the *W*-statistic at the 95% level of confidence.

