9.4.6 PLANNED INTERIM ANALYSES

Tabular outputs and/or listings will be provided at all available timepoints (baseline, Day 28, Day 56, Day 84) (1) participant preference surveys and questionnaires; (2) participant demographics; (3) reported adverse events; and, (4) concomitant medications.

Additionally, an interim analysis will be conducted after the Day 28 visit data has been collected for approximately 50% of participants in each of Cohorts 1 and 2. The interim analysis will include the following assessments data:

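### Section 9.4.3 gives CGI-I at Day 28 a paired change-from-baseline test, but CGI-I has no baseline and no stated reference value, so step 2 of the hierarchy cannot be run as written

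*Combined protocol and SAP*

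**What the plan says.** Section 9.4.3 of the protocol states: "The following secondary efficacy endpoints will be tested using the same technique outlined for the primary efficacy analysis". It then lists three items: the change in ADHD-RS, the CGI-I score at Day 28, and the change in TOVA scores.

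The technique referred to is set out in Sections 9.1 and 9.4.2. It is a two-sided paired t-test on a difference "defined for each participant as the score measured on Day 28 minus the score measured at the baseline visit", with a null mean of 0. A Wilcoxon signed rank test replaces it if skewness exceeds 1.5 in magnitude. Participants without a baseline value are excluded. Section 9.4.2 adds a decision rule: "If the upper bound of the 95% confidence interval is smaller than 0 in a particular cohort, we will conclude that significance is achieved".

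CGI-I is the second secondary step in each cohort, after the IRS and ADHD-RS. Section 9.4.3 continues: "If the test for (2) is significant at the 0.05 confidence level, the test for (3) change in TOVA constituents" goes ahead, through seven named TOVA scores in order. On error control it says: "Within each cohort, the maximum allowable Type I error rate will be set to 0.05".

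**The concern.** A paired test needs two values of the same measure for each child, and CGI-I has only one by Day 28. The endpoint wording in the Synopsis and Section 3 reflects this: ADHD-RS and TOVA are defined as changes, and CGI-I as a score. The analysis wording in 9.4.3 does not carry the distinction through.

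CGI-I is a step in a confirmatory sequence with seven TOVA tests behind it. If the step's result does not depend on whether children improved, a significant CGI-I result says nothing about improvement. Depending on which decision rule is applied, the TOVA tests are then either always released or never released at that point.

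CGI-I is also among the data for the interim look in Section 9.4.6, which covers both cohorts: "an interim analysis will be conducted after the Day 28 visit data has been collected for approximately 50% of participants in each of Cohorts". The reference value should therefore be on record before that look.

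**Working it through.** **1. Can the stated test be formed?** In the Schedule of Activities (Section 1.3), the CGI-I row is marked at Days 28, 56 and 84 only. The baseline visit has CGI-S, a different item, and no section names it as the comparator. Section 9.4.8 lists CGI-I among tables at each available timepoint, baseline included, but that is a generic list and does not create a baseline CGI-I. No participant has a Day 28 minus baseline difference.

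**2. Is there another test in the text?** Section 9.1's signed rank fallback also needs differences from a null value. Section 9.4.1 offers a paired t-test, which fails for the same reason, and a chi-square or Fisher test. A chi-square goodness-of-fit test can be run on one sample, but it needs reference proportions, and none are given. Section 8.1 only names the instrument. Section 9.4.1 settles sidedness ("Unless otherwise indicated, comparisons will always use a two-sided significance test at the 95% level of confidence") but not the value to test against.

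**3. Sample sizes used below.** Section 9.2 plans 117 and 66 evaluable participants. With n = ((1.960 + 1.282)/ES)², rounded up, ES 0.30 gives 117 and ES 0.40 gives 66. Both match the plan.

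**4. What happens if the raw score is tested against 0?** The coding is not in the documents, so three codings are shown as assumptions. With no true improvement, the mean equals the no-change value c, and t = c·√n/SD. The main figure is for SD 1; brackets give SD 1.5 to SD 0.8.

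| Assumed coding | c | t at n=117 | t at n=66 |
|---|---|---|---|
| 1 to 7 | 4 | 43.3 (28.8–54.1) | 32.5 (21.7–40.6) |
| 0 to 6 | 3 | 32.4 (21.6–40.6) | 24.4 (16.2–30.5) |
| −3 to +3 | 0 | expected 0; valid at 5% | expected 0; valid at 5% |

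The critical values are 1.98 and 2.00.

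**5. Is the result truly fixed under 1–7 coding?** For scores between 1 and 7 with mean m, t is smallest when every score is 1 or 7, giving t = m·√(n−1)/√((m−1)(7−m)). The minimum is at m = 1.75 and equals 0.882·√(n−1): 9.5 at n=117 and 7.1 at n=66. That extreme data set has skewness of about 2.3, so Section 9.1 would send it to the signed rank test. There every value lies above 0 and the exact p is 2·0.5ⁿ, below 10⁻¹⁹ at both sizes. On either branch p<0.05 is certain. An upper confidence bound below 0 is impossible, because the mean is at least 1.

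**6. Behaviour against the no-change value.** In a simulation of 5,000 runs per case (rounded normal scores, SD 1, clipped to 1–7), the test against 0 gave p<0.05 in 100% of runs and an upper bound below 0 in 0%, for every true mean from 3.0 to 5.0. Against 4, the upper bound fell below 4 in 2.9% (n=117) and 2.3% (n=66) of runs at a true mean of 4.0, and in 87% and 62% at 3.7. Tested against its no-change value, the step responds to improvement.

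**The case against.** The strongest reply is that the gap is a missing number and not a wrong method. A paired t-test is a one-sample t-test on a change measure, CGI-I is itself a rating of improvement, and the null in Section 9.1 is no mean change. Most statisticians would test CGI-I against its no-change point, and the separate SAP that Section 9 promises is where such a value would be expected. Much of this stands: the repair keeps the same family of tests, and the SAP may already contain the value. But 9.4.3 as worded calls for a difference that cannot be computed, and the documents reviewed do not supply the value that would replace it.

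A reader might infer that the step has no valid null under any coding. That goes too far: if no change is coded 0 with improvement negative, a test against 0 is correct. The unconditional point is that the reference value is unstated.

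A reader might also infer that the trial carries a 100% false-positive rate. It does not. CGI-I is tested formally only after IRS and ADHD-RS are both significant, so if nothing improves, the primary test alone holds a formal CGI-I claim to about 5% or less. The fixed result bites where those two pass and CGI-I shows no improvement.

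Nor do the documents show that the value will be chosen after data are seen; the SAP's date and content are unknown.

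**Conclusion.** The point holds in a limited form. The test that 9.4.3 assigns to CGI-I cannot be run as written, because there is no baseline CGI-I and no stated reference value. This rests on the text alone.

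The size of the consequence depends on the assumed coding. On an all-positive scale tested against 0, the p<0.05 criterion in 9.4.3 is always met, whereas the upper-bound rule in 9.4.2, if read as part of the same technique, is never met. On a scale centred at 0 there is no distortion.

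The effect is confined to the CGI-I claim and to what happens after it. It is tempting to read this as inflated type I error for TOVA, but that does not follow. If step 2 always opens, the TOVA tests simply follow IRS and ADHD-RS in fixed order at 0.05. If it never opens, they are reported with nominal p-values only. The primary endpoint, the ADHD-RS test and the sample size are untouched. The wording should be fixed because it sits at a confirmatory step and costs little to correct.

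**What to change.** In 9.4.3, take CGI-I out of the shared-technique sentence and add, before any CGI-I data are reviewed (including at the interim analysis):

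*CGI-I at Day 28 will be compared with the scale's no-change value [sponsor to state coding and value] by a two-sided one-sample t-test at 0.05, or by a Wilcoxon signed rank test of score minus that value if skewness exceeds 1.5 in magnitude. The step is passed only if p<0.05 and the estimate lies on the improvement side of that value.*

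If the separate SAP already sets a null for CGI-I, reconcile 9.4.3 with it. The cost is one or two sentences, with no new visits, data or participants.
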